FEAST and ultrabrief RUL ECT patients will be treated identically except as noted below. The traditional d'Elia electrode placement will be used for UB RUL ECT (American Psychiatric Association, 2001), with the frontotemporal electrode tangential to the midpoint of the line connecting the right auditory tragus and the canthus. The posterior electrode will be tangential to the vertex (midpoint of line connecting nasion and inion). Standard stainless steel 2" diameter electrodes will be used. If it is deemed that patients require a change in ECT modality, a switch to either brief pulse RUL or BL ECT will be implememnted, as clinically indicated.

B.8 Assessment of Efficacy

Clinician ratings. Instruments include the HRSD (24-item) (Hamilton, 1967), MADRS (Montgomery and Asberg, 1979), CGI (severity and improvement) (Guy, 1976), and the GAS (Endicott and Spitzer, 1978). A clinical evaluation team independently completes these scales on the basis of conjoint interviews, both at set time points (preECT baseline, 1-2 days after ECT termination) and the HRSD alone is also completed at spaced intervals (weekly during the ECT course). Interviews usually take place between 10 AM-12 PM to minimize variability due to diurnal variation.

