An identical titration schedule is used at the first treatment in all patients. Seizure threshold, quantified at the first treatment (in mC) will be \log_{10} transformed to achieve normal distributions, with adequacy of fit tested. An ANCOVA will be conducted on these values with Site (MUSC vs. GRU) and Treatment Group (FEAST vs. UB RUL ECT) as between-subject factors, and age and gender as covariates. Second order interactions will be modeled for the covariates. Gender and age were selected since they have repeatedly shown association with ST (Boylan et al., 2000, Krueger et al., 1993, [name] et al., 1987c, [name] et al., 1987d, [name] et al., 2008).

Hypothesis 2. In quantitative 4-lead ictal EEG measures, FEAST results in (a) less intense seizure expression (i.e., reduced amplitude especially in low frequency bands) and (b) less postictal suppression, than UB RUL ECT. In addition, the FEAST group will manifest (c) marked asymmetry in the ictal EEG as expressed in greater amplitude (total power) in right relative to left hemisphere leads. With EEG leads over traditional frontal sites and novel temporal sites, FEAST will show a pattern of (d) greatest EEG seizure expression at the right prefrontal site. In contrast, the group treated with a bidirectional stimulus and a conventional electrode configuration (UB RUL ECT) will have (e) less of a gradient between the hemispheres and in the anteroposterior plane. Quantitative measures of (f) seizure expression and postictal suppression have no or weak relations with efficacy.

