The four-lead EEG digitized at each treatment will be subjected to a FFT after artifacting, and power computed in 4 frequency bands, as well as total power across bands. The baseline, tonic, clonic and postictal epochs will be averaged separately. After testing for multivariate normality, MANCOVAs will be applied to the ictal and postictal power (\log_{10}) values, using Site and Treatment Group as between-subject factors, and age as a covariate. Hypotheses 2a and 2b call for opposite main effects in the ictal and postictal analyses. Hypotheses 2c and 2e predict an interaction between Treatment Group and the laterality repeated measures factor. Thus, an asymmetry index $[(r-l)/(r+l)]$ will be greater with FEAST than conventional stimulation. Similarly, Hypotheses 2d and 2e calls for an interaction between Treatment Group and frontal vs. temporal lead placement. Finally, Hypothesis 2f states that measures of ictal and postictal power have at most weak relations with efficacy. Percent change

in HRSD₂₄ scores will be added to the MANCOVAs as a covariate. Main effects of clinical improvement and first and second-order interactions will be modeled.

Hypothesis 3. In contrasting resting fMRI data, both FEAST and UB RUL ECT result in a reduction of (heightened) frontal connectivity, replicating previous findings (Abbott et al., 2013, Beall et al., 2012, Perrin et al., 2012). However, this effect is especially focal within the FEAST group, and more restricted to right frontal regions.

MANCOVAs will be conducted with Site and Treatment Group as between-subject factors, age as a covariate, and time (pre-post) and connectivity values in a priori brain regions as repeated measures factors.

Hypothesis 4. Efficacy as assessed immediately following the treatment course does not differ between the FEAST and UB RUL ECT groups.

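### Hypothesis 2c claims right-over-left ictal asymmetry within FEAST, but its only named test is the between-group interaction it shares with 2e

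*Combined protocol and SAP*

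**What the plan says.** Section IV.B.15 words Hypotheses 2a and 2b as comparisons with UB RUL ECT. The form then changes: 2c predicts that FEAST itself will show "marked asymmetry in the ictal EEG as expressed in greater amplitude (total power) in right relative to left hemisphere leads". The reference for 2c is FEAST's own left hemisphere. The comparator enters in 2e, where the UB RUL ECT group is predicted to have "less of a gradient between the hemispheres and in the anteroposterior plane".

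The analysis paragraph that follows fits MANCOVAs to log10 ictal and postictal power, "using Site and Treatment Group as between-subject factors, and age as a covariate", with laterality as a repeated measure. It then gives the two hypotheses one shared test: "Hypotheses 2c and 2e predict an interaction between Treatment Group and the laterality repeated measures factor". This is read as an asymmetry index, (r-l)/(r+l), that "will be greater with FEAST than conventional stimulation".

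The section names no laterality effect within FEAST, no test of the index against zero, and no threshold for calling an asymmetry marked.

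**The concern.** The hypothesis and its test have different nulls. For 2c the null is that right and left power are equal in FEAST. For the Treatment Group by laterality interaction the null is that the right-left difference is the same in both groups. Neither implies the other.

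This matters because some asymmetry in the comparator is plausible on the plan's own terms. UB RUL ECT is right-sided stimulation (Section B.7: "with the frontotemporal electrode tangential to the midpoint of the line connecting the right auditory tragus and the canthus"), and 2e predicts a smaller gradient in that group, not its absence. If the two asymmetries turn out similar, a null interaction would be read against 2c even though FEAST seizures were clearly lateralised. If the interaction is positive, 2c would be declared supported by a result that does not address it.

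Section II lists characterising the focal nature of seizure onset with FEAST and with RUL ECT as an objective. Section IV.B.15 says the study is to yield effect sizes for a later randomised trial. Both call for each group's own asymmetry as well as the difference.

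**Working it through.** The plan gives no power, alpha or effect size for Hypothesis 2, so there is no stated figure to reproduce. The calculation below only shows how the two tests can diverge.

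**Inputs**
- Group sizes: 40 FEAST and 40 UB RUL ECT completers (Section B.1).
- Level: two-sided 0.05, assumed. A result counts only when significant in the predicted direction.
- Asymmetry: each patient's right-minus-left log power, with mean dF in FEAST and dR in UB RUL ECT, in units of a common SD. These values are assumed. Site and age are ignored.

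**Formulas** (noncentral t)
- Within-FEAST contrast: df = 39, critical t = 2.023, noncentrality = dF × √40.
- Interaction: df = 78, critical t = 1.991, noncentrality = (dF − dR) × √(40/2).

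The interaction depends only on dF − dR. The within-FEAST contrast depends only on dF.

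**Worked case, dF = 0.8 and dR = 0.4**
- Within-FEAST: 0.8 × √40 = 5.06, power 99.9%.
- Interaction: 0.4 × √20 = 1.79, power 42%.

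**Results**

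| FEAST (dF) | UB RUL (dR) | Gap | Interaction | Within-FEAST |
|---|---|---|---|---|
| 0.8 | 0.8 | 0 | 2.5% | 99.9% |
| 0.8 | 0.4 | 0.4 | 42% | 99.9% |
| 1.0 | 0.5 | 0.5 | 60% | about 100% |
| 1.0 | 0.25 | 0.75 | 91% | about 100% |
| 1.5 | 0.5 | 1.0 | 99% | about 100% |
| 2.0 | 1.0 | 1.0 | 99% | about 100% |

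The 2.5% in the first row is one tail of the assumed level, because the true interaction there is zero. A gap of about 0.63 SD gives roughly 80% power for the interaction.

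In the second and third rows FEAST has twice the asymmetry of UB RUL ECT, in line with both 2c and 2e. The only test named for 2c still misses in 58% and 40% of trials respectively.

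The converse is a matter of logic. With dF = 0 and dR = −0.5 the gap is again 0.5, so the interaction is positive in 60% of trials although FEAST has no asymmetry. Nothing in the documents makes left-dominant UB RUL ECT likely. The case shows only that a positive interaction does not entail 2c.

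**The case against.** The strongest reply is that the EEG question is comparative throughout. Section B.13 states the primary aim as a contrast of FEAST with UB RUL ECT, and the EEG predictions in the introduction to the investigational plan and in Section B.6 are worded the same way. On that view 2c and 2e are two halves of one contrast, and the interaction is the right test of it. If UB RUL ECT is equally lateralised, a null result rightly counts against FEAST being the more focal treatment. All of this stands for 2e and for the primary aim. It does not supply a test of 2c as written. If only the comparison is meant, 2c needs rewording.

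A reader might infer that the interaction fails whenever UB RUL ECT is also asymmetric, however marked the FEAST asymmetry. That is not so. It loses power only when the two asymmetries are close. At a fixed UB RUL level, a larger FEAST asymmetry raises its power, to 99% at 1.5 against 0.5.

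A reader might also infer that the trial could not tell a non-lateralised FEAST from two equally lateralised treatments. The documents do not support that either. The index is signed and laterality is in the model, so group means would show the pattern informally. What is missing is a named estimate and the rule for reading it.

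Finally, a contrast against zero shows some asymmetry, not marked asymmetry; it has 87% power at only 0.5 SD. That is fair, and it is why the interval matters more than the p-value.

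**Conclusion.** The point holds in limited form. 2c is a within-FEAST claim whose only specified test is a between-group interaction, and that test neither establishes nor refutes it. The primary EEG comparison is not compromised.

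The practical size depends on how close the two asymmetries are: large when they are similar (2.5% or 42% for the interaction against 99.9% within FEAST) and negligible when they differ by about 1 SD. These figures rest on an assumed two-sided 0.05 level, equal SDs, assumed effect sizes and no covariate adjustment. The mismatch of nulls rests on none of these. The change should be made, because the stated test does not match the stated hypothesis and the remedy uses the same model and data.

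**What to change.** In Section IV.B.15, separate the two tests.

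- **2c:** the within-FEAST contrast of right minus left log10 total ictal power from the same model, adjusted for site and age, with its 95% CI. The interval lets the size of the asymmetry be judged, since the plan sets no threshold for marked.
- **UB RUL ECT:** report the same within-group estimate and interval.
- **2e:** keep the Treatment Group by laterality interaction and the between-group comparison of the asymmetry index.
- **Reading rule:** a statement that FEAST is asymmetric rests on the 2c contrast; a statement that it is more asymmetric than UB RUL ECT rests on the interaction.

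The cost is a few lines of analysis-plan wording and one extra contrast, with no new data. The small downside is one more named test within Hypothesis 2, which should be counted in the restricted set of primary analyses that the section promises.

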Medication Status. Patients will be stabilized on their medications for 7 days and will be withdrawn from lithium and anticonvulsants for at least 5 days. ECT starts after completion of the baseline battery, usually after an additional 1-2 days. PRN lorazepam is limited to 3 mg/d, and is withheld approximately 10 hr before a treatment. A daily log is kept of all medications (psychotropic or otherwise) patients receive. Introduction of any medication during the FEAST (or UB RUL ECT) will be considered a protocol violation but will not lead to termination from the study.

General Treatment Technique. After completion of the pretreatment assessment battery, treatment with FEAST will begin. FEAST will be administered only with the modified Spectrum 5000Q device approved with this IDE application. Treatments are given in the morning, 3 times per week. Pharmacological agents are standardized: atropine (0.4 mg IV), methohexitol (0.75 mg/kg) and succinylcholine (0.75-1.0 mg/kg). [If methohexitol is unavailable, thiopental is substituted (2.0 mg/kg).] Patients are oxygenated by mask (100% O₂) prior to anesthesia and until resumption of

spontaneous respiration. Standardized procedures are used to reduce impedance at FEAST and EEG electrode sites. The impedance of the EEG electrodes is kept ~ 5k ohms.

The "cuff technique" assists in monitoring the duration of ictal motor activity (Fink and Johnson, 1982). The EEG sites are left and right frontal (F7 and F8) and a custom placement for the left and right temporal leads (to avoid overlap with the RUL ECT electrodes). Each EEG site is referenced to the ipsilateral mastoid (Weiner and Krystal, 1993). A detailed manual is available that describes detailed procedures for preparing the FEAST or RUL ECT electrode sites and the EEG sites. As indicated the primary hypothesis tested in this study concerns the ictal EEG collected at every treatment. We predict that seizure onset will be more restricted to the right frontal site with FEAST compared to UB RUL ECT.

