The primary aim of this study is to contrast FEAST and UB RUL ECT in these EEG measures of seizure onset and propagation. Specifically, we expect FEAST to show greater focality of seizure onset than UB RUL ECT, with seizure onset most manifest in the right frontal EEG with FEAST, and far greater activity in the left and right temporal leads with UB RUL ECT.

B.14 Quality Assurance and Data Management

A highly experienced rater will provide clinical ratings throughout the treatment period. Accuracy of the output of the FEAST device will be tested ([name] et al., 1994), and calibration signals regularly applied to the EEG recordings. The stimulus parameters used with the modified Spectrum 5000Q will both be recorded electronically and transferred to a database using the Spectrum's automatic EMR logging software. An experienced psychometrician will review all neurocognitive data. Data will be entered on digital forms using automatic flags for out-of-range and missing values. Any correction to a data record will be recorded in an audit notebook. The study database will be backed-up regularly.

B.15 Statistical Analyses

Data Screening. Data will be reviewed for extreme values. When distributional assumptions are not met, data will be transformed or nonparametric procedures used. Prior to statistical analyses, the study sites (MUSC vs. GRU) and treatment groups (FEAST vs. UB RUL ECT) will be compared in the baseline sociodemographic and clinical features, using ANOVA and log-linear analyses, with a liberal threshold to detect inequality ($P < 0.2$).

Hypothesis Testing. Even though this is a preliminary investigation, yielding effect sizes by which to power a subsequent randomized study, it is important to protect the Type I error rate by limiting primary analyses to a restricted and clearly specified set of hypotheses and outcome measures. The primary analyses will test the hypotheses stated below which address the objectives described in Section II. The major areas of investigation are effects on seizure threshold, electrophysiological (EEG) activity, efficacy, function, objective changes in cognition and subjective cognitive changes. The primary efficacy analyses will be conducted in the intent-to-treat sample.

Hypothesis 1. FEAST is substantially more efficient (i.e., lower ST) than traditional ECT, even when both use an ultrabrief (0.3 ms) pulse width.

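### The group by frontal-versus-temporal interaction assigned to Hypothesis 2d cannot show that seizure expression under FEAST is greatest at the right frontal lead

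*Combined protocol and SAP*

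**What the plan says.** Section IV.B.6 describes a two-by-two layout of leads: "The EEG sites are left and right frontal (F7 and F8) and a custom placement for the left and right temporal leads". Section IV.B.13 gives the EEG comparison its status: "The primary aim of this study is to contrast FEAST and UB RUL ECT in these EEG measures of seizure onset and propagation". It then states the expected result, "with seizure onset most manifest in the right frontal EEG with FEAST", and adds that UB RUL ECT should show much more activity at both temporal leads.

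In Section IV.B.15, Hypothesis 2 makes a claim about one lead: "FEAST will show a pattern of (d) greatest EEG seizure expression at the right prefrontal site".

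The analysis text that follows uses MANCOVAs on log10 ictal and postictal power, "using Site and Treatment Group as between-subject factors, and age as a covariate". It assigns tests to the sub-hypotheses as follows:

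- Laterality: "Hypotheses 2c and 2e predict an interaction between Treatment Group and the laterality repeated measures factor", with an asymmetry index in support.
- Region: "Similarly, Hypotheses 2d and 2e calls for an interaction between Treatment Group and frontal vs. temporal lead placement".
- Higher-order terms are mentioned only for 2f, where percent change in HRSD24 enters as a covariate: "Main effects of clinical improvement and first and second-order interactions will be modeled".

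The text ties no group by laterality by region term, no right frontal contrast and no comparison of leads within FEAST to 2d.

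**The concern.** Hypothesis 2d ranks one lead above three others. The assigned test compares the average of two frontal leads with the average of two temporal leads, and asks whether that difference is larger with FEAST. A positive answer is compatible with a right frontal focus, but also with patterns in which the right frontal lead is unchanged, or in which the left frontal lead is the one that rises.

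Right frontal restriction of seizure onset is the prediction that Section IV.B.6 singles out when it describes the primary hypothesis, and it is part of the primary aim in Section IV.B.13. If 2d is declared supported on this term alone, the report could claim right frontal focality that the data do not show. The study is also meant to supply effect sizes for a later randomized trial, so the estimate carried forward would be of something other than the stated claim.

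**Working it through.** The plan gives no power, SD or effect size for the EEG hypotheses, so there is no figure to reproduce.

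**Step 1: contrasts (no assumed figures).** Let RF, LF, RT and LT be the FEAST minus UB RUL differences in mean log10 power at the right frontal, left frontal, right temporal and left temporal leads.

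- Group x region = (RF + LF)/2 − (RT + LT)/2
- Group x laterality = (RF + RT)/2 − (LF + LT)/2
- Group x laterality x region = (RF − LF) − (RT − LT)

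Now let FEAST differ from UB RUL ECT at one lead only, by an amount d:

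| Pattern | Group x region | Group x laterality | Three-way | RF − LF | RF − RT | RF − LT |
|---|---|---|---|---|---|---|
| Right frontal +d | +d/2 | +d/2 | +d | +d | +d | +d |
| Left temporal −d | +d/2 | +d/2 | −d | 0 | 0 | +d |
| Right temporal −d | +d/2 | −d/2 | +d | 0 | +d | 0 |
| Left frontal +d | +d/2 | −d/2 | −d | −d | 0 | 0 |

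The term assigned to 2d is the same in all four rows. The laterality term removes the last two. The first two rows agree on both planned interactions and separate only on the three-way term and the single-lead contrasts.

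**Step 2: size under assumed inputs.** Group size: 40 per group (the protocol overview before Section IV.B, and Section IV.B.1). Assumed, because the documents give none: two-sided 0.05, lead-level SD 0.25 log10, independent leads.

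Each two-way contrast has weights of ±1/2 on four leads, so its SD is √(4 × 0.25 × 0.25²) = 0.25. The SE of the group difference is 0.25 × √(2/40) = 0.056. A shift of 0.3 at one lead gives a contrast of 0.15, and 0.15/0.056 is about 2.7, so power is about 76%. That figure applies equally to all four rows of the table.

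By simulation, a left temporal shift of −0.4 makes both planned interactions positive in 89% of trials, a shift of −0.3 in 57%.

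**Step 3: sensitivity.** With a between-lead correlation of 0.5 and a left temporal shift of 0.8 lead SDs, the group x region term is positive in about 70% of simulated trials, and both interactions in 49%. A right frontal increase of the same size gives the same figures. For a left temporal shift of 0.5 to 1.0 SD and correlations of 0.3 to 0.8, the power of the group x region term runs from 27% to over 99%. The percentages move with the assumptions; the equality of the patterns does not.

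**Step 4: group comparison versus ranking within FEAST.** Suppose FEAST means are 1.0 at left frontal and 0.9 at right frontal, and UB RUL means are 1.0 and 0.5. The group difference in right minus left frontal is (0.9 − 1.0) − (0.5 − 1.0) = +0.4, yet the right frontal lead is not the highest in FEAST. A between-group contrast therefore cannot establish 2d alone, because 2d is worded as a ranking within FEAST.

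**The case against.** The best defence is that the interaction tests something the study does predict. Section IV.B.13, the protocol overview before Section IV.B, and Section III.D.2 all expect less temporal activity with FEAST, and frontal versus temporal is a sensible contrast for that. This stands. A reader might infer that a left temporal difference would give spurious support to the whole primary aim. The documents do not bear that out: lower left temporal activity is itself part of what is predicted. The gap is confined to the right frontal element.

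A reader might also infer that the planned analysis is weak when a right frontal focus is real, since both interactions are positive in only about 57% of trials for an excess of 0.3. But the plan does not require both. The term assigned to 2d is positive in about 76%.

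Two further defences carry some weight. A repeated-measures MANCOVA would normally print the three-way term and the lead means, so a careful report could avoid the misreading; but the plan ties that term to no hypothesis and gives it no direction. And the study is open-label, non-randomized and preliminary, with no stopping decision resting on 2d. That lowers the severity. Section IV.B.15 nevertheless justifies limiting the primary analyses to a clearly specified set of hypotheses in order to protect Type I error, and here the hypothesis and its test do not match.

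**Conclusion.** The concern holds for Hypothesis 2d and for the right frontal prediction in Sections IV.B.6 and IV.B.13. The assigned test cannot distinguish a right frontal increase from three other single-lead patterns, one of which, a left frontal increase, runs against the claim. With the laterality interaction added, a left temporal decrease still cannot be told apart from a right frontal increase. A significant group x region term would be evidence for the frontal-versus-temporal prediction only.

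This conclusion is exact. How often it would mislead cannot be stated from the documents: every percentage above rests on an assumed SD or standardized shift, between-lead correlation and significance level. Severity: should be fixed before analysis.

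**What to change.** In the Hypothesis 2 analysis text of Section IV.B.15:

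1. Keep the two two-way interactions for 2c, 2e and the frontal-versus-temporal prediction.
2. For 2d, require within FEAST that log10 ictal power at the right frontal lead exceeds that at the left frontal, right temporal and left temporal leads, with all three contrasts significant at 0.05 in the predicted direction. This is an intersection-union test, so it needs no multiplicity penalty.
3. Report the same three contrasts compared between groups, with the group x laterality x region term, as the evidence that right frontal focality is greater with FEAST than with UB RUL ECT.

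This needs no new recordings or epochs. The cost is a stricter rule. Its power within FEAST cannot be given, because the documents report no lead-level means or SDs. If the three-contrast rule were applied between groups, under the Step 2 assumptions, it would do better than the planned term for a right frontal excess of 0.3 alone (about 91% against 76%). It would do worse if the effect were additive gradients of 0.15 in each direction, that is, group differences of 0.30 right frontal, 0.15 left frontal, 0.15 right temporal and 0 left temporal (about 30% against 76%). The revised plan should state this trade-off.

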The protocol presented in this new IDE will be performed at two clinical sites (MUSC and GRU). At each site 20 patients will be recruited to receive treatment with FEAST, or a total of 40 FEAST patients across the sites. A contemporaneous group of 20 patients will be identified at each site who are receiving standard clinical treatment with UB RUL ECT. These patients will be matched to the FEAST sample (within site)

in the distribution of gender and diagnosis (unipolar vs. bipolar), and the mean, variance and shape of the distributions of age and baseline modified mini-Mental State score (mMMS) (Stern et al., 1987). This RUL cohort is also included under this IDE. [We considered but ultimately abandoned having a formal, blind randomization of patients to FEAST or RUL. While we ultimately hope to perform such a study, the data with FEAST are quite limited at present. There thus may not be true clinical equipoise. Similarly, although the FEAST side effects appear benign, there have still been less than 50 patients total ever treated with FEAST. We thus have settled on a non-randomized but loosely matched comparison group. This group is important for the analysis of the EEG and MRI data, and can also be used for rough comparison of efficacy and cognitive side effects. It is our hope that following this trial, there might be sufficient evidence of efficacy to enable a formal randomized definitive trial.

We will be applying to the NIH for funding to support the conduct of this protocol. This IDE will serve to gather important pilot data and will serve as the IDE for the NIH study, if it is funded.

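### Hypothesis 2f predicts at most a weak link between ictal EEG and efficacy, but its only planned analysis is an ordinary covariate test, which cannot support that claim

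*Combined protocol and SAP*

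**What the plan says.** Section IV.B.15 introduces its hypotheses with the sentence "The primary analyses will test the hypotheses stated below which address the objectives described in Section II". Hypothesis 2 has six parts. Parts (a) to (e) are predictions about EEG differences between FEAST and ultrabrief right unilateral ECT. Part (f) differs in kind: it predicts that quantitative measures of "seizure expression and postictal suppression have no or weak relations with efficacy". The analysis paragraph restates this as "measures of ictal and postictal power have at most weak relations with efficacy".

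That paragraph first sets out MANCOVAs on log10 ictal and postictal power, "using Site and Treatment Group as between-subject factors, and age as a covariate", and assigns 2a to 2e to main effects and interactions in them. For 2f it then says that percent change in HRSD24 "scores will be added to the MANCOVAs as a covariate", and "Main effects of clinical improvement and first and second-order interactions will be modeled". Nothing further is given for 2f. The section describes the study as "yielding effect sizes by which to power a subsequent randomized study", but does not connect that aim to 2f.

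**The concern.** Hypothesis 2f is a claim of absence, or near absence, of a relation. The planned analysis looks for evidence that a relation exists. Because 2f tolerates a weak relation, neither outcome decides it. A significant coefficient could still be weak. A non-significant one could come from a relation that most readers would not call weak. Without a numerical meaning for weak, the report will have to judge 2f after the results are seen.

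What is at stake is the interpretation of one secondary mechanistic statement. Hypotheses 2a and 2b predict less intense seizure expression and less postictal suppression with FEAST. Whether those features track clinical benefit is something a later randomized trial would want as an estimate with its uncertainty, not as a bare P value.

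**Working it through.** The documents give no alpha, margin, power or sample-size calculation for 2f, so there is no stated figure to reproduce.

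**Inputs from the documents**
- FEAST group: "a total of 40 FEAST patients across the sites" (study overview ahead of Section IV.B).
- Comparison group: 40 patients (Section IV.B.1). Total n = 80.
- Maximum enrolment: 60 + 60 = 120 (Section IV.B.1).
- Model terms named: site, treatment group, age (Section IV.B.15).

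**Assumptions**
- Two-sided alpha 0.05. The only threshold in the section, P < 0.2, is for baseline comparisons.
- One EEG measure, with the relation expressed as a partial correlation r.
- k = 4 terms partialled out: the three named, plus one more such as site by group.

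**Scale.** By Fisher's z, atanh(r) has standard error 1/sqrt(n - 3 - k). With n = 80 and k = 4, sqrt(73) = 8.544.

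**Power to detect a relation**, Phi(atanh(r) x 8.544 - 1.960):
- r = 0.20: 0.2027 x 8.544 = 1.732; Phi(-0.228) = 0.41.
- r = 0.30: 0.3095 x 8.544 = 2.645; Phi(0.685) = 0.75.
- r = 0.40: 0.4236 x 8.544 = 3.620; Phi(1.660) = 0.95.

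A true r of 0.20 would therefore be missed about 59% of the time, and 0.30 about 25%. A simulation of the partial-correlation t-test gave 0.41 and 0.76 at 0.20 and 0.30. With no terms partialled out (k = 0) the formula gives 0.43 and 0.78, so k matters little.

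**What a non-significant result leaves open**
- Observed r = 0: 95% limits are ±tanh(1.960/8.544) = ±tanh(0.2294) = ±0.225, about -0.23 to 0.23.
- Observed r just short of significance, about 0.225: upper limit tanh(0.2294 + 0.2294) = 0.43.

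**What a bound would deliver.** If the 90% interval must lie inside ±m (two one-sided tests at 5%), the chance of success when true r = 0 is 2 x Phi(atanh(m) x 8.544 - 1.645) - 1:
- m = 0.30: 2 x Phi(1.000) - 1 = 0.68.
- m = 0.20: 2 x Phi(0.087) - 1 = 0.07.

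With a 95% interval and m = 0.30 it is 2 x Phi(0.685) - 1 = 0.51. With n = 120 and k = 4 (sqrt(113) = 10.63), power to detect 0.20 and 0.30 is 58% and 91%, and the chance of meeting the 0.30 bound with a 90% interval is 90%.

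**The case against.** The strongest reply is that the study is openly preliminary, that 2f allows a non-zero relation, and that the plan never says a non-significant result will be taken as proof of none. All of that is correct. A reader might infer such a rule from the absence of any other, but it is not written. The gap is that no rule of any kind is given.

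The primary status of 2f can also be disputed. The primary analyses are tied to the objectives in Section II, which cover efficacy, cognition, safety and focality and do not mention an association between EEG and efficacy. The opening sentence of the hypothesis section nonetheless includes every hypothesis listed below it.

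Several stronger readings are tempting and should be set aside:
- **That a non-significant result is to be expected even if the relation is moderate.** At n = 80, power is about 75% at r = 0.30 and 95% at 0.40, so the test would usually detect it. The description fits r near 0.20.
- **That precision should be worked out on 40 patients.** The plan fits one model to both groups and specifies no within-group correlation.
- **That 2a to 2e are distorted because HRSD24 change, a post-treatment outcome, sits in their model.** The paragraph reads most naturally as a base model for 2a to 2e that is then extended for 2f. The wording could be clearer, but this is not an error.
- **That 2f is used to justify limiting seizure spread.** No section says so. Hypothesis 4 addresses efficacy directly, and Section IV.C.2 looks ahead to a randomized trial.

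Finally, a single r is a simplification of a MANCOVA with several leads and frequency bands.

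**Conclusion.** The point holds in a limited form. Hypothesis 2f asserts at most a weak relation, and the planned covariate test cannot establish that whether or not it is significant. At the planned 80 patients, non-significance would be compatible with correlations up to about 0.23 in either direction when the estimate is zero, and up to about 0.43 when it falls just short of significance.

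These sizes rest on my assumptions of two-sided 0.05, one EEG measure and four partialled terms. The 0.30 and 0.20 bounds are illustrative, since the plan offers none. The consequence is confined to how one sub-hypothesis is reported, so this is a worthwhile refinement and does not threaten the study's main comparisons.

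**What to change.** In Section IV.B.15, for Hypothesis 2f:
1. Name the EEG measures to be used, and report the partial association of each with HRSD24 change, with its confidence interval.
2. Pre-state a numerical bound for weak, chosen by the sponsor (for example |partial r| < 0.30), and the interval level.
3. Conclude at most weak only if the interval lies wholly inside the bound; otherwise report the result as inconclusive.
4. State that Hypotheses 2a to 2e are tested in the base MANCOVA without HRSD24 change.

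This is a wording change using data already collected. The cost is that inconclusive becomes a likely outcome. With a 0.30 bound and a 90% interval the criterion is met about 68% of the time at n = 80 even when the true correlation is 0, so at least about 32% of the time the answer would be inconclusive. A 0.20 bound would be met only about 7% of the time. If the sponsor does not want to set a bound, labelling 2f as exploratory estimation and reporting the intervals would also be sound.
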